#### 4.3 Number of Participants

184. We will need to recruit 68 patients who are found to have endometriosis at laparoscopy, and 116 who are not.

#### 4.4 Study sites

Patients who are already planning to undertake laparoscopic surgery (for any indication) with any of the investigators will be invited to participate. AL and ABS consult with patients in St Leonards, and operate at The Mater hospital (North Sydney), North Shore Private Hospital (St Leonards), and the Royal North Shore Hospital (St Leonards). [name] operates at Strathfield Private Hospital (Strathfield) and Concord Hospital (Concord). A/[name] operates at Nepean Hospital (Kingswood). The surgical processes and procedures at each of these hospitals are very similar, with minute differences only in regards to the surgical equipment utilised.

The BCL6 laboratory analysis will be performed at the Douglass Hanly Moir laboratory in Macquarie Park

# 4.5 Expected Duration of Study

It is expected that it will take approximately nine months to undertake this study, with recruitment beginning as soon as ethical approval and funding have been received. We expect that it will take approximately six months from the commencement of recruitment through to performing the operations on all participants. We expect statistical analysis and writing of any related reports and journal articles to take an additional three months.

### 4.6 Outcome Measures

Participants will be asked to fill out an online version of the long form of the EHP-30 questionnaire, which is a reliable, validated instrument to measure the health-related quality of life of women with endometriosis.

Participants' endometrial biopsy samples will be sent to the Douglass Hanly Moir laboratory for BCL6 analysis.

*BCL6 as an endometriosis biomarker* Protocol Version 5, 26/08/2021 Page 15 of 47

Clinicians will use the r-ASRM classification system to score participants' endometriosis intraoperatively (please see Appendix 13.1). This involves documenting and scoring patients': endometriotic implants (that are seen at laparoscopic surgery) based on their location and size, the location and thickness of any adhesions (bands of scarring between internal organs); plus the extent to which the 'Pouch of Douglas' (the area between the uterus and bowel) is involved. Patients will then end up being classified as having either: no endometriosis; stage I (minimal); stage II (mild); stage III (moderate); or stage IV (severe) endometriosis.

#### **5 STUDY TREATMENTS**

Some participants in this study would already be planning to undertake endometrial biopsy, in addition to planned laparoscopy (for example, to investigate heavy menstrual bleeding). Others may originally only be planning to undertake laparoscopy, and will (if they participate) undergo an endometrial biopsy (as part of this study), over and above the planned laparoscopy.

While the patient is anaesthetised, endometrial biopsy will be performed using a 'dilatation and curettage' technique. This involves:

- Gently dilating the cervical canal up to 5mm diameter, using 'cervical dilators'
- Using a 'curette' to take a sample of the lining of the uterus ('endometrium')

This procedure is outlined in the attached 'Patient information and consent' form, as are the potential complications, including:

- Uterine perforation (approximately 1 in 300 women)
- Formation of intra-uterine adhesions (scar tissue) (approximately 1 in 60 women)
- Cervical injury (approximately 1 in 25 women)
- Infection (approximately 1 in 20 women)
- Blood loss > 100mLs (approximately 1 in 10 women)

(Please see Appendix 13.2 for this document.)

The potential implications of the above possible complications and their management include:

(1) Uterine perforation: collection of blood tests for full blood count; injury to bladder or bowel

(1 in 15 patients who have a uterine perforation); intra-abdominal haemorrhage (1 in 6
patients who have a uterine perforation); need for laparotomy (very rare)

*BCL6 as an endometriosis biomarker* Protocol Version 5, 26/08/2021 Page 16 of 47

- (2) Intra-uterine adhesions: lighter menstruation (4 in 5 women with intra-uterine adhesions); sub-fertility (1 in 8 women with intra-uterine adhesions); cyclic pelvic pain (1 in 30 women with intra-uterine adhesions); recurrent pregnancy loss (1 in 8 women with intra-uterine adhesions). Management of the above issues involves hysteroscopy (a procedure performed under general anaesthetic to visualise the lining of the uterus with a small video camera), and resection of the intra-uterine adhesions (separating the intra-uterine scarring, using 'diathermy' electrosurgical devices).
- (3) Cervical injury: repair of any cervical tear is performed immediately, using several absorbable stitches.
- (4) Infection: mild infections (the majority) are treated with tablet antibiotics; severe infections (very rare) require admission to hospital and intravenous antibiotics.
- (5) Blood loss > 100mLs: observation; collection of blood tests for full blood count; administration of medications such as syntocinon and/or tranexamic acid; in the cases of very rare major haemorrhage (> 1000mLs), laparotomy (open surgery) may be needed

The above potential complications of dilatation and curettage can be compared with the potential risks of laparoscopic surgery, which include the following:

- Conversion to an open operation ('laparotomy') (approximately 1 in 70 women)
- Injury to urinary tract (bladder or ureters) (approximately 1 in 100 women)
- Injury to major (big) blood vessel (approximately 1 in 200 women)
- Injury to minor (small) blood vessel (approximately 1 in 350 women)
- Later development of hernia through one of the scars (approximately 1 in 500 women)
- Injury to gastrointestinal tract (stomach or bowels) (approximately 1 in 1000 women)

After the endometrial biopsy tissue has been sent to Douglass Hanly Moir (DHM) pathology laboratories, they will be analysed to assess the BCL6 level. DHM then routinely stores all pathology slides and paraffin block for ten years. After this point, samples are incinerated.

#### **6 PARTICIPANT ENROLLMENT AND RANDOMISATION**

#### 6.1 Recruitment

Patients are referred to our gynaecology clinics by other clinicians (e.g. general practitioners, other gynaecologists, fertility specialists) for a range of gynaecological complaints and conditions, including: pelvic pain, pelvic organ prolapse, leiomyomata, endometriosis, ovarian cysts, infertility, heavy menstrual bleeding, and urinary incontinence. All patients who fulfil the inclusion criteria (as outlined below) will be invited to participate.

#### 6.2 Eligibility Criteria

Inclusion criteria will be:

- Women aged between 18 50yo
- Women who have a regular menstrual cycle (i.e. menstrual cycle length 21 35 days inclusive)
- Women who are already planning to undertake laparoscopy, for any indication
- English speaking
- Capacity and willingness to give written informed consent
- Willingness to comply with the study
- Willingness to have their planned procedure undertaken in the luteal phase of their menstrual cycle

## Exclusion criteria will include:

- Women aged < 18yo or > 50yo
- Women with an irregular menstrual cycle (i.e. menstrual cycle length < 21 days or > 35 days)
- Women who have an absolute contra-indication to endometrial biopsy, such as viable (ongoing) intra-uterine pregnancy
- Women who have a relative contra-indication to endometrial biopsy, such as: active cervical or uterine infection
- Women in whom undertaking an (otherwise unnecessary) endometrial biopsy may worsen a pre-existing condition (e.g. Asherman's syndrome, intra-uterine adhesions)

Women with an unwanted / non-viable pregnancy will also be excluded, as the potential risks of undertaking a dilatation and curettage in that context are significantly higher than in a non-gravid (not pregnant) uterus. A urinary pregnancy test will be completed immediately pre-operatively (i.e. on the day of the planned operation, in the pre-operative / admission area of the relevant hospital), to exclude any pregnant women.

#### 6.3 Informed Consent Process

Potential participants will be given the attached 'Patient Information and Consent' form at least two weeks prior to their planned procedure to read at their leisure (please see Appendix 13.2). This outlines the potential risks of undertaking an endometrial biopsy.

Prior to their planned procedure, they will be given the opportunity to clarify their understanding with a clinician not associated with this study (e.g. surgical assistant or consultant anaesthetist). They will then be invited to sign the attached 'Patient Information and Consent' form.

### 6.4 Enrolment Procedure

Participants will be enrolled into the study after the informed consent process has been completed (as above), and the participant has met all inclusion criteria and none of the exclusion criteria. The participant will receive a study enrolment number; thereafter, all of their data will be linked with this enrolment number only.

## 6.5 Blinding Arrangements

The surgeons who classify participants' endometriosis intra-operatively will not yet have the result of their BCL6 endometrial biopsy. The pathologists who determine participants' BCL6 result will be blinded as to participants' endometriosis severity.

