At their planned procedure, endometrial biopsy will be taken, using the standard dilatation and curettage method. As a guide, approximately 0.5cm3 of tissue will be biopsied, weighing approximately 2 grams. The endometrial biopsy sample will be sent to the laboratory for analysis of the BCL6 level. Laparoscopy will be undertaken (as planned), and the patient's endometriosis (if present) will be scored. Clinicians will use the best-known, and most widely used, classification system for endometriosis: the revised American Society for Reproductive Medicine (r-ASRM) classification system (please see Appendix 13.1). This involves documenting and scoring patients' endometriotic implants (seen at laparoscopy) based on their location and size, the location and thickness of any adhesions (internal scarring), plus the extent to which the 'Pouch of Douglas' (the area between the uterus and bowel) is involved. Patients will then end up being classified as having either: no endometriosis; stage I (minimal); stage II (mild); stage III (moderate); or stage IV (severe) endometriosis.

*BCL6 as an endometriosis biomarker* Protocol Version 5, 26/08/2021 Page 14 of 47

Later statistical analysis will aim to determine to what extent patients' BCL6 levels (on luteal phase endometrial biopsy) is predictive of the presence and severity of endometriosis at laparoscopy. Additional analysis will include patients' EHP-30 results as a predictive variable, to assess if the combination of BCL6 level plus EHP-30 answers improves the predictive value of these two screening tools for endometriosis.

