#### 11 DATA MANAGEMENT

#### 11.1 Data Collection

'RedCap' will be used to develop an online version of the long-form EHP-30 questionnaire. Participants will complete this questionnaire online, pre-operatively.

Participants' BCL6 results will be analysed and collated at the Douglass Hanly Moir pathology laboratories by AF and SCB, and forwarded on to ABS in due course.

Participants' endometriosis severity will be classified intra-operatively by the relevant surgeon, according to the r-ASRM classification system. These results will be documented immediately post-operatively into the participant's 'case report form' (CRF). The hard copy of the CRF will be given to the Principal Investigator by hand, and the data entered into 'RedCap'.

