#### 11.2 Data Storage

All data will be stored in an Excel spreadsheet, on a NSLHD server. Only two authors (ABS and AL) will have access to the source data and the Excel spreadsheet.

Each participant will be allocated a 'enrolment number' in chronological order, based upon their operation date and time. Thereafter, their data (EHP-30 results, BCL6 result, endometriosis severity) will be stored based on their enrolment number only.

The Excel spreadsheet that links each participant's name with their unique enrolment number will be stored on a password-protected computer on a NSLHD served, and will only be accessible to ABS and AL.

The hard copies of the CRFs will be stored in a locked filing cabinet at the Centre for Advanced Reproductive Endosurgery, for fifteen years after the last related publication.

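### The staging surgeon is kept from the BCL6 result but not from the EHP-30 answers, and two investigators who operate have access to those answers

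*Protocol*

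**What the plan says.** Protocol section 6.5 has two blinding rules. For surgeons: "The surgeons who classify participants' endometriosis intra-operatively will not yet have the result of their BCL6 endometrial biopsy". For pathologists: "The pathologists who determine participants' BCL6 result will be blinded as to participants' endometriosis severity". Neither mentions EHP-30.

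EHP-30 is nevertheless a predictor under test. Secondary objective 2 (section 3.2) asks whether adding it to BCL6 improves prediction of the presence, absence or severity of endometriosis. Section 4.2 says: "Additional analysis will include patients' EHP-30 results as a predictive variable", and asks whether the combination "improves the predictive value of these two screening tools for endometriosis". Section 10.3 plans a logistic and multivariable model for this, possibly shown as a nomogram or classification tree.

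On timing, section 11.1 says of the EHP-30: "Participants will complete this questionnaire online, pre-operatively". On the outcome, the same section says: "Participants' endometriosis severity will be classified intra-operatively by the relevant surgeon, according to the r-ASRM classification system".

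On access, section 11.2 says that only two authors "will have access to the source data and the Excel spreadsheet". It lists EHP-30 results among the stored data, and gives the same two people the file linking names to enrolment numbers. Section 4.4 describes both as seeing patients and operating.

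**The concern.** When a predictor is tested against a reference standard, whoever assigns the reference standard should not know the predictor's value. Section 6.5 applies this to BCL6, whose result does not exist at the time of staging. It does not apply it to EHP-30, whose answers do.

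The line between case and control leaves room for judgement. In the r-ASRM table (section 15 and the case report form), one superficial peritoneal implant under 1 cm scores 1 point, and stage I starts at 1 point. A single doubtful lesion can therefore turn a control into a case. The case report form records no histology that would check that call.

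If a surgeon who has read a high EHP-30 score is readier to call such a lesion endometriosis, part of the link between EHP-30 and endometriosis is created by the staging. Secondary objective 2 and any nomogram or tree built on it would then favour EHP-30. Analysis cannot repair this afterwards, because the influence is already in the outcome.

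**Working it through.** The protocol states no figure on this point, so the main check sets the sections side by side.

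1. **Is EHP-30 a predictor under test?** Yes (3.2, 4.2, 10.3).
2. **Do the answers exist before staging?** Yes (4.2, 11.1).
3. **Does any section withhold them from the staging surgeon?** No. Section 6.5 names only BCL6 for surgeons.
4. **Can anyone who stages see them?** Two investigators can. Section 11.2 gives them the source data and section 4.4 says they operate. Storage under an enrolment number does not mask them, because they hold the link file.
5. **Does this cover every surgeon?** No. Section 4.4 names further investigators operating at Strathfield Private, Concord and Nepean, and section 11.2 gives them no access.
6. **Does the case report form pass on the answers?** No. It has a tick box for completion only.
7. **Is the primary comparison touched?** No. It concerns BCL6, and section 6.5 covers both directions there.

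**Illustration of direction and scale (assumed rates).** From section 10.1, prevalence p = 1/3 × 10% + 2/3 × 50% = 36.7%. Suppose EHP-30 has no true link to endometriosis. Let f_H and f_L be the fractions of truly negative women called positive among those above and below the median EHP-30 score.

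Odds of a positive call = (p + (1 − p)f) / ((1 − p)(1 − f)), and the odds ratio (OR) is the value at f_H divided by the value at f_L.

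| f_H | f_L | Odds, high score | Odds, low score | OR |
|---|---|---|---|---|
| 10% | 10% | 0.430/0.570 = 0.754 | 0.754 | 1.00 |
| 10% | 7% | 0.754 | 0.411/0.589 = 0.698 | 1.08 |
| 10% | 5% | 0.754 | 0.398/0.602 = 0.662 | 1.14 |
| 20% | 15% | 0.493/0.507 = 0.974 | 0.462/0.538 = 0.858 | 1.14 |
| 10% | 0% | 0.754 | 0.367/0.633 = 0.579 | 1.30 |

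Half of 184 is 92 women above the median, of whom 0.633 × 92 = 58.3 are truly negative. A 5-point difference is then about 0.05 × 58.3 = 2.9 women.

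The ratio exceeds 1 whenever f_H is above f_L, so the bias favours EHP-30. Its size depends on the difference caused by reading the form, which the protocol does not give. The table also treats EHP-30 alone, so it does not measure value added to BCL6.

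**The case against.** The strongest reply is that exposure is possible but not described. No section says that a surgeon reads the answers before staging. Section 10 sends them to statistical software for analysis, and section 11.2 is about storage and confidentiality. This stands: the point is that nothing prevents the exposure, not that it will happen.

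The second reply is that the surgeon already knows much of what EHP-30 would tell. The surgeons with access see these patients in clinic, and section 10.1 takes suspicion of endometriosis as known before surgery, with 50% against 10% expected prevalence. In odds that is (0.5/0.5)/(0.1/0.9) = 9. Hiding the questionnaire removes only what it adds to that knowledge. This also stands, and is why the effect may be small. It does not justify also showing the surgeon the exact variable that enters the model.

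Three stronger readings are tempting:

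- A reader might infer that the main result is compromised. It is not, since the BCL6 comparison is blinded in both directions.
- A reader might infer that all operating surgeons hold the data. Only two are given access.
- A reader might infer a large excess of false-positive findings for EHP-30. That needs a high rate of over-calling in high scorers, none in low scorers, and all of the difference attributed to reading the form. The protocol supports none of these.

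**Conclusion.** The gap is real but limited. For patients staged by the two investigators with data access, the protocol lets the assessor of a visual reference standard see a predictor that will be tested against it. Any resulting bias in secondary objective 2 would be upward, provided that a high score makes the surgeon readier to call a doubtful lesion positive.

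The size cannot be derived from the protocol. The odds ratios of 1.08 to 1.30 rest on assumed over-calling rates and show scale only; the true effect may be near nil. The point calls for an inexpensive improvement in conduct and casts no doubt on the primary objective. It belongs in the protocol, which has its own sections on blinding and access, because it must be settled before staging.

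**What to change.** - **Section 6.5:** add that operating surgeons do not view EHP-30 answers before the r-ASRM score has been recorded.
- **Section 11.2:** amend the access rule so that the RedCap rights of the two investigators show only whether the EHP-30 is complete, until all r-ASRM scores have been entered. The Synopsis describes an automatic upload of answers from RedCap to Excel. That upload should wait until the same point, because the two investigators can open the spreadsheet.
- **Limitation:** state that surgeons know the clinical history and indication, and that this cannot be masked.

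The answers are needed only for the later analysis, so no record-by-record release and no extra staff are required. The cost is a permission setting and a few sentences. The downside is that the two investigators cannot read the questionnaire before surgery.

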# 6.6 Participant Withdrawal

Participants are able to withdraw from the endometrial biopsy part of the study up until they are anaesthetised. Should any participants ask to withdraw from the study pre-operatively, endometrial biopsy will not be undertaken.

Should they later decide that they want to withdraw from the study, their data can be removed from the database up until the point of analysis.

#### 6.7 Trial Closure

All participants will receive follow-up through our private gynaecology clinic. This involves: a telephone call from our clinic nurse at approximately 1 week post-operatively (henceforth known as 'follow-up 1'); and two phone calls at approximately 4 weeks post-operatively ('follow-up 2'). One phone call will be from the Principal Investigator, to explain to the patient the stage of endometriosis (if present), and their BCL6 HSCORE. The other phone call will be from the clinic nurse, to ask if they have experienced any complications, such as uterine perforation, fever, or post-operative haemorrhage. If any patient reports any complications, the nurse will escalate immediately to the Principal Investigator.

Should any patient have any concerns post-operatively, they are welcome to call our clinic to discuss these concerns over the phone, and/or to come in for consultation.

#### 7 STUDY VISITS AND PROCEDURES SCHEDULE

List of interventions	Enrolment Visit	Day of procedure	Follow-up 1	Follow-up 2
Patient information sheet discussed	✓	✓		
Consent signed		✓		
Inclusion / exclusion criteria discussed	✓	✓		
Stage of endometriosis classified		✓		
Adverse event and serious event assessment			✓	~
Stage of endometriosis discussed with participant				√

#### 8 CLINICAL AND LABORATORY ASSESSMENTS

Patient's BCL6 results on their endometrial biopsy samples will be analysed at Douglass Hanly Moir pathology laboratories, based in Macquarie Park.

Formalin-fixed, paraffin-embedded tissue blocks will be sectioned at 4 mm. Slides will be stained with haematoxylin-eosin, and consecutive sections stained with antibodies against BCL6 (clone GI191E/A8; Cell Marque, Rocklin, California). Immunohistochemistry will be performed on an automated system by a certified Pathology Laboratory (Douglass Hanly Moir, Macquarie Park, Sydney) using the Ventana Benchmark Ultra Auto-immunostainer platform (Roche Diagnostics). Antigen retrieval will be performed with Tris based buffer (CC1, Roche Dianostics, Arizona). Positive immunoreactivity (Brown precipitate) will be detected using the OptiView DAB Detection Kit (Roche Diagnostics, Arizona) A positive control of lymph node will be included. The semiquantitative assessment of expression will be made using the HSCORE (0-4), calculated using the following equation: HSCORE . P Pi (i . 1)/100, where i . intensity of staining with a value of 1, 2, or 3, (weak, moderate, or strong, respectively) and Pi is the percentage of stained epithelial cells for each intensity, varying from 0% to 100%.

The use of an automated system for immunostaining will reduce a potential bias in immunohistochemical analysis; this automated system will be read by a gynaecologic pathologist [either Adj. [name] (AF), or [name] (SCB)].

Participants' endometriosis severity will be classified intra-operatively according to the r-ASRM: this is the standard scoring system for endometriosis. This involves documenting and scoring patients': endometriotic implants based on their location and size, the location and thickness of any adhesions (internal scarring), plus the extent to which the 'Pouch of Douglas' (the area between the uterus and bowel) is involved (please see Appendix 13.1). Patients will then be classified as having either: no endometriosis; stage I (minimal); stage II (mild); stage III (moderate); or stage IV (severe) endometriosis

